7. BACKGROUND AND SIGNIFICANCE

Hypothesis 1a (acute pain): Pain within the first week after a mastectomy or limb amputation is often intense, with breakthrough pain as measured with a Numeric Rating Score (NRS; 0-10, 0 = no pain, 10 = extreme pain) a median of 7; and 25% of women describing a “continuous aching pain” the day following mastectomy.¹ Similarly, pain following knee and shoulder arthroplasty, rotator cuff repair, video-assisted thoracoscopic surgery, and burn-related skin grafting also can result in significant postoperative pain. Intense analgesia may be provided with a peripheral nerve block, which involves the placement of long-acting local anesthetic adjacent to the peripheral nerves that innervate the surgical site.² Unfortunately, the longest-acting local anesthetics clinically available have a duration of less than 24 hours, after which patients are mainly dependent upon opioids, which result in inadequate analgesia and undesirable side effects such as pruritis, nausea, vomiting, constipation, urinary retention, sedation, and respiratory depression. Local anesthetic-based analgesia may be extended using a continuous perineural infusion via a percutaneous catheter; but, this technique is usually limited to a few days due to infection risk, catheter dislodgement, and anesthetic consumption.³ The pain of these surgical procedures can last weeks, and is often exacerbated by physical therapy, itself critical to optimizing outcomes following knee and shoulder surgery.

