9. RESEARCH DESIGN AND METHODS

All subjects would continue to receive standard and customary postoperative analgesics, so there is no risk of subjects receiving a lower degree of analgesia than if they otherwise did not enroll in the study. The cryoneurolysis procedure will be done in addition to our current UCSD standard practice.

Study Overview

Day 0 Subjects randomized and cryoneurolysis/sham procedure administered

Days 0-4, 7, 14, 21 Pain levels, opioid consumption, and other end points collected [inspiratory spirometry for hospitalized subjects following video-assisted thoracoscopic surgery will occur at various time points as part of standard care and will be collected via EPIC]

Months 1, 3, 6, 12 Brief pain inventory administered [range-of-motion measurements following knee and shoulder arthroscopy as well as rotator cuff repair will occur at various time points as part of standard care and will be collected via EPIC]

Year 3 Cancer recurrence investigated for subjects with cancer-related procedures

Subjects will be individuals undergoing unilateral or bilateral mastectomy; upper or lower limb amputation; primary, unilateral total knee or shoulder arthroplasty; primary, unilateral rotator cuff repair; video-assisted thoracoscopic surgery; and burn-related skin grafting of the lateral thigh. Those who consent to participate in this study will have standard preoperative peripheral nerve blocks administered and catheters inserted: paravertebral blocks or a fascial plane block (e.g., erector spinae plane block) for mastectomy, femoral/sciatic for lower limb amputation, brachial plexus (or terminal nerves) for upper limb amputation; femoral or adductor canal for total knee arthroplasty; interscalene for shoulder arthroplasty or rotator cuff repair; thoracic epidural for video-assisted thoracoscopic surgery (VATS); and lateral femoral cutaneous nerve for skin grafting of the lateral thigh.

Treatment group assignment (randomization). Subjects with successfully-administered peripheral nerve blocks (defined by sensory changes in the appropriate nerve distribution) will be allocated to one of two possible treatments:

1. *cryoneurolysis*
2. *sham cryoneurolysis (placebo control)*

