Cryoneurolysis probes are available for a console neurolysis device (PainBlocker, Epimed, Farmers Branch, Texas) that either (1) pass nitrous oxide to the tip inducing freezing temperatures; or, (2) vent the nitrous oxide at the base of the probe so that no gas reaches the probe tip, resulting in no temperature change. Importantly, these probes are indistinguishable in appearance, and therefore treating physicians, subjects, and all clinical staff will be masked to treatment group assignment [only the physician/investigator performing the cryoneurolysis will be unmasked]. An angiocatheter/introducer may be inserted beneath the ultrasound transducer and directed until the probe tip is immediately adjacent to the target nerve (lidocaine 2% will be administered, as needed, to anesthetize the angiocatheter track). The angiocatheter needle will be removed, leaving the angiocatheter through which the appropriate Epimed probe will be inserted until it is adjacent to the target nerve. The cryoneurolysis device will be triggered using 3 cycles of 2-minute gas activation (active or sham) separated by 1-minute defrost periods. For active probes, the nitrous oxide will be deployed to the tip where a drop in temperature to -70°C will result in cryoneurolysis. For the sham probes, the nitrous oxide will be vented prior to reaching the probe shaft, resulting in a lack of perineural temperature change. The process will be repeated with the same treatment probe for any additional nerves (e.g., all nerves will receive either active cryoneurolysis or sham/placebo, and not a mix of the two possible treatments).

FDA Approval. Cryoneurolysis has been FDA approved since May 28, 1976, with continuous clinical use since then. The specific device used for this study, the Epimed Painblocker, has been FDA cleared for use to treat both acute and chronic pain since April 30, 1986, as a significant risk device. The Painblocker is NOT considered experimental or investigational (there is no IDE); and, we are using the device in a manner that the FDA approved of regarding the subject population and purpose (treating acute pain).

Outcome measurements (end points). Staff blinded to treatment group assignment will perform all measures and assessments, which will include:

Pain: measured on the 11-point NRS of pain intensity

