Brief Pain Inventory: The Brief Pain Inventory (short form) is an instrument specifically designed to assess pain and its impact on physical and emotional functioning within the previous 24 hours.^{22,23} It has established reliability and validity, with minimal inter-rater discordance, and is recommended by

the Initiative on Methods, Measurement, and Pain Assessment in Clinical Trials (IMMPACT) consensus statement.²⁴ The Brief Pain Inventory is comprised of three domains: (1) *pain*, with four questions involving “worst”, “average”, “least”, and “current” pain levels using a 0-10 Numeric Rating Scale (NRS; 0 = no pain; 10 = worst pain imaginable); (2) percentage of *relief* provided by pain treatments with one question (reported score is the percentage divided by 10 and then subtracted from 10: 0 = complete relief, 10 = no relief); and, (3) *interference* with 7 questions involving physical and emotional functioning using a 0-10 Likert scale (0 = no interference; 10 = complete interference). The use of both single items (e.g., average pain) and the composite score (0 = optimal; 120 = worst possible) is supported by the IMMPACT recommendations for assessing pain in clinical trials.²⁵⁻²⁷

Opioid consumption

Sleep disturbances: due to surgical pain

Range of motion: measured with a standard goniometer

Forced expiratory volume in 1 second (FEV1): measured with a standard inspiratory spirometer

Cancer recurrence: for subjects who underwent the surgical procedure related to a primary cancer, subjects' records will be investigated for indications of cancer recurrence up to 3 years following catheter placement (including estrogen receptor status as + or -). Patients may be contacted by phone if records suggest that the patient has not returned to the original surgeon within the previous 12 months.

The questionnaire will differentiate among multiple dimensions of breast and limb pain:

Phantom pain: painful sensations referred to the lost body part (breast or limb).

Phantom breast/limb sensations: non-painful sensations referred to the lost body part.

Wound pain: painful sensations localized to the portion of the body still present.

Summary of post-enrollment assessments (color added for clarity)

Time Point:	Postoperative Days								Postoperative Months			
	0	1	2	3	4	7	14	21	1	3	6	12
Opioid consumption	•	•	•	•	•	•	•	•	•	•	•	•
Average & worst pain [NRS]	•	•	•	•	•	•	•	•				
Brief Pain Inventory									•	•	•	•
Average & worst phantom pain									•	•	•	•

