Incidence; duration each episode									•	•	•	•
Average & worst wound pain									•	•	•	•
Incidence; duration each episode									•	•	•	•

Difficulty sleeping due to pain?	•	•	•	•	•	•	•				
Awakenings due to pain	•	•	•	•	•	•	•				
Nausea (0=none, 10=vomited)	•	•	•	•	•	•	•				

* In addition to the above, for knee and shoulder surgery joint range of motion will be measured at various time points between 1-12 months as part of standard postoperative care; and for VATS, FEV1 will be measured at various time points during hospitalization as part of standard postoperative care.

Statistical Analysis. The limb amputation, total knee and shoulder arthroplasty, rotator cuff repair, VATS, and skin grafting subjects will be included in pilot studies to help power future clinical trials, so we will enroll a convenience sample and not have a pre-determined primary endpoint or statistical plan. However, the end points of most interest will be average pain score on postoperative day 2 for shoulder arthroplasty and skin grafting subjects, range-of-motion at 6 weeks for the rotator cuff repairs, range-of-motion for knee arthroplasty, and FEV1 for the VATS procedures.

For the subjects having mastectomy, we will power this study for an acute pain end point which will provide conclusive results for that end point; but, the data will also be used to help power a subsequent large, multicenter clinical trial for a chronic pain-related end point (which will require far more subjects than we will enroll for the current study).

For the mastectomy subjects, sample size calculations are centered around the hypothesis that cryoneurolysis decreases the incidence and severity of post-mastectomy pain in the week following surgery. To this end, the primary outcome is the average NRS (as administered as part of the Brief Pain Inventory) queried on the afternoon of postoperative day 2. The difference in the distribution of NRS between groups will be assessed using the Mann-Whitney U test. We approximate power using the two-sample t-test. Assuming a standard deviation of 2.25 NRS points,² and minimum clinically meaningful difference of 2 NRS points, n=30 patients per group provide 86% power with two-sided $\alpha=5\%$.

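### Is it unclear which day-2 pain score is the mastectomy primary outcome, since the Brief Pain Inventory is scheduled only from month 1?

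*Combined protocol and SAP*

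**What the plan says.** All the governing text is in Section 9 of the combined protocol and SAP, apart from one line in Section 7.

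- **Statistical Analysis.** For mastectomy, "the primary outcome is the average NRS (as administered as part of the Brief Pain Inventory) queried on the afternoon of postoperative day 2". The groups are compared with the Mann-Whitney U test.
- **Study Overview.** The early contacts read "Days 0-4, 7, 14, 21 Pain levels, opioid consumption, and other end points collected". The later ones read "Months 1, 3, 6, 12 Brief pain inventory administered".
- **Assessment table.** The row "Average & worst pain [NRS"] is marked in all eight day columns and no month column. The Brief Pain Inventory row is marked in all four month columns and no day column.
- **Outcome measurements.** Two entries appear. The first is "Pain: measured on the 11-point NRS of pain intensity", with no anchors or recall period. The second is the inventory, described as "designed to assess pain and its impact on physical and emotional functioning within the previous 24 hours". Its four pain questions (worst, average, least, current) record "levels using a 0-10 Numeric Rating Scale (NRS; 0 = no pain; 10 = worst pain imaginable"). The same paragraph cites consensus support for using either individual items, with average pain as its example, or the composite.
- **Section 7, Background.** The abbreviation is first introduced as "Numeric Rating Score (NRS; 0-10, 0 = no pain, 10 = extreme pain"), in a sentence reporting published pain levels.

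**The concern.** A primary outcome should be traceable from its definition to a cell in the schedule. Here the definition names the inventory, and the inventory has no day-2 cell. The two measures are listed separately, and nothing says outright that the early row borrows the inventory's item, anchors or recall period. The two upper anchors in the document add to the impression of two different scales.

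If the two texts did describe different measurements, one coordinator could give the full inventory on day 2 while another asked only two questions. The primary score of the only powered cohort would then mix item wordings. Average pain on day 2 and at months 1 to 12 might also not be readable on one scale.

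**Working it through.** No figure in the plan depends on this point, so the check is to set the texts side by side and ask what would be recorded and analysed under each reading.

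**1. Is the mismatch real?** Counting table marks:

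| Row | Day columns (0, 1, 2, 3, 4, 7, 14, 21) | Month columns (1, 3, 6, 12) |
|---|---|---|
| Average and worst pain | 8 of 8 | 0 of 4 |
| Brief Pain Inventory | 0 of 8 | 4 of 4 |

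The two rows share 0 of 12 time points. The Study Overview gives the inventory's timing in prose and agrees, so this is not damage from PDF extraction.

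**2. Does zero overlap show two rival instruments?** No. The inventory has 4 pain + 1 relief + 7 interference = 12 items, and 12 × 10 = 120, which matches the stated composite maximum. Average and worst pain are two of the four pain items. Once the whole inventory is given, a separate row for those two would be redundant. Zero overlap is what one expects if the early row is a subset of the inventory.

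**3. Which single reading fits all the text?** The average-pain item asked alone in the early period, with the full inventory from month 1. On this reading the parenthesis in the primary-outcome sentence identifies the item. It fits the row label, the paragraph allowing single items, and the Overview.

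**4. Does the recall period break this reading on day 2?** No. Surgery is on day 0. Twenty-four hours back from the afternoon of day 2 is the afternoon of day 1, wholly after surgery. A 24-hour window on day 0 would reach back before surgery, but day 0 is not the primary time point.

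**5. Do the anchors conflict?** Only across sections. The sole anchors in the methods are those of the inventory items. The other wording is in background text that summarises published pain levels and does not define this trial's measure.

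**6. What changes between the readings?**

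| Feature | Average item asked alone | Average item within the full inventory |
|---|---|---|
| Score analysed | one 0-10 average pain score | one 0-10 average pain score |
| Time | afternoon of day 2 | afternoon of day 2 |
| Assessor | masked, same question in both arms | masked, same question in both arms |
| Test | Mann-Whitney U | Mann-Whitney U |
| Design inputs | difference 2, SD 2.25, 30 per group | difference 2, SD 2.25, 30 per group |

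Every entry is the same, so power is the same under both readings. (The stated 86% does not follow from SD 2.25, for which a two-sided t-test gives 92.3%. It follows from SD 2.5, the value in the plan's simulation, which gives 86.1%. That is a separate matter and does not bear on which item is asked.)

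**The case for a change.** The best case for a change is that this is the primary outcome of the one cohort that the plan says will give a conclusive answer, and a primary outcome should not need interpretation. Taken literally, the sentence says the inventory is administered on day 2, and no schedule entry supports that. Day-2 average pain is also named as the end point of most interest for shoulder arthroplasty and skin grafting, so the same row serves several surgery types. A clause in the definition or a row label would cost almost nothing.

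What stands is that the sentence and the table do not match as written, and that the recall period of the early row must be inferred. The rest is weaker. Whether staff would ask different things depends on the case report forms, which are not among the documents. Reading day 2 and later months on one scale serves no planned analysis, because the plan has only between-group comparisons. Even if staff did vary in how they asked, they are masked, so the variation would not track treatment. Giving the full inventory on day 2 would take that contact from 2 pain items to 12, a real burden that would leave the score analysed unchanged.

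**Conclusion.** The mismatch is a clerical slip that calls for no change to the plan. The day-2 score is scheduled, it is a 0-10 average pain rating under either reading, and it goes into the same test with the same 30 patients per group. The effect on bias, power and the between-group comparison is nil. An analyst with the data would find one average-pain value per patient on day 2 and would use it.

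This rests on two assumptions. The first is that the day-2 row is the inventory's average-pain item asked alone, which the row label and the single-item paragraph support but do not state. The second is that the case report form puts the same question to both arms, which the masking of assessors makes reasonable.

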The t-test approximation was confirmed by simulating integer valued NRS scores in the range 0 to 10. One group was simulated by rounding normally distributed data with mean 1.5 and standard deviation 2.5 (resulting in median of 2 and interquartile range 0 to 3); and the other with mean 3.5 and standard deviation 2.5 (resulting in median of 4 and interquartile range 1 to 5). Note these resulting summary statistics are consistent with Ilfeld et al (2014). When 10,000 trials were simulated under these assumptions, the Mann-Whitney U test provided 89.5% power, and Type I error was maintained at 4.85%.

Differences between groups in demographic variables and secondary endpoints will be assessed with the Mann-Whitney U test for continuous or ordinal data, and Fisher's Exact test for categorical data. Box-and-whisker plots will be used to visualize distributions by group.

R version 3.4.4 ([R-project.org](https://www.R-project.org)) was used for sample size calculations and simulations; and the most recent version of R will be used at the time of analysis.

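### The two power figures for the mastectomy endpoint do not match the SDs printed beside them, and one simulated quartile is wrong

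*Combined protocol and SAP*

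**What the plan says.** The mastectomy cohort is the only one with a powered endpoint: average pain score on postoperative day 2, compared by the Mann-Whitney U test. Its sample size rests on two calculations in the Statistical Analysis part of section 9.

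- **t-test.** "We approximate power using the two-sample t-test". The inputs are "Assuming a standard deviation of 2.25 NRS points" and "minimum clinically meaningful difference of 2 NRS points". The result is that "n=30 patients per group provide 86% power with two-sided" alpha of 5%.
- **Simulation.** "The t-test approximation was confirmed by simulating integer valued NRS scores in the range 0 to 10". One group is a rounded normal with mean 1.5 and SD 2.5, reported as median 2 and interquartile range 0 to 3. The second is "the other with mean 3.5 and standard deviation 2.5 (resulting in median of 4 and interquartile range 1 to 5"). Of these summaries the plan says "Note these resulting summary statistics are consistent with" the earlier trial that it cites. The result is: "When 10,000 trials were simulated under these assumptions, the Mann-Whitney U test provided 89.5% power", with a type I error of 4.85%.

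The plan does not explain why the two calculations use different SDs, and it does not say whether the simulated test was one- or two-sided.

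**The concern.** The contradiction shows before anything is recomputed. Sample size and mean difference are the same in both calculations, yet the rank test at the larger SD is credited with 3.5 points more power (89.5 − 86) than the t-test at the smaller SD. For near-normal data a larger SD should lower power, and the rank test should do slightly worse than the t-test. At least one printed pair of SD and power must be wrong, so the simulation cannot confirm the t-test figure.

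These two figures are the whole justification for 30 per group on the one endpoint that the plan calls conclusive. The intended type II error matters when a null result is interpreted, and the assumed SD matters to anyone planning the follow-on multicenter trial from these data.

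**Working it through.** **Inputs**, all from the Statistical Analysis part of section 9: n = 30 per group; difference 2; two-sided 5%; SD 2.25 for the t-test; rounded normals with means 1.5 and 3.5 and SD 2.5, limited to 0–10, for the simulation. Stated powers are 86% and 89.5%.

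**1. t-test.** Power comes from the noncentral t distribution with 58 degrees of freedom, critical value 2.002, and noncentrality 2 / (SD × √(2/30)).

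| SD | Noncentrality | Power | Stated |
|---|---|---|---|
| 2.25 (as printed) | 2 / (2.25 × 0.2582) = 3.443 | 92.3% | 86% |
| 2.5 | 2 / (2.5 × 0.2582) = 3.098 | 86.1% | – |

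The normal approximation gives 93.1% and 87.3%, so the choice of formula does not explain the gap. Solving for the SD that yields 86% gives 2.505. At SD 2.25, 24 per group already gives 85.4% and 25 per group gives 86.9%.

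**2. Mann-Whitney simulation.** Rounded normals, 30 per group, tie- and continuity-corrected, two-sided 5%, 100,000 trials (Monte Carlo SE about 0.1 point).

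| SD | Out-of-range values set to 0 or 10 | No bounds | Stated |
|---|---|---|---|
| 2.5 (as printed) | 82.7% | 83.9% | 89.5% |
| 2.25 | 90.0% | 90.6% | – |

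The Monte Carlo SE of the plan's own 10,000-trial estimate is √(0.895 × 0.105 / 10,000) = 0.3 point, so a gap of 6 to 7 points is not noise. Other constructions at SD 2.5 do not reach 89.5% either:

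- without continuity correction: 83.0%
- rounding down: 82.1%
- rounding up: 83.1%
- redrawing out-of-range values: about 68%, which also makes the lower group's interquartile range 1 to 4 against the printed 0 to 3

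The recomputed type I error is 4.7–4.9%, in line with the stated 4.85%. A one-sided 5% test at SD 2.5 with bounds gives 89.8%.

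**3. Exchanging the SDs.** The t-test at SD 2.5 gives 86.1% (stated 86%). The simulation at SD 2.25 gives about 90% (stated 89.5%). Both printed figures are then recovered to within about half a point with bounded scores.

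**4. Quartiles of the mean-3.5 group.** A rounded score is at most k when the normal value is below k + 0.5.

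| | SD 2.25 | SD 2.5 |
|---|---|---|
| P(score ≤ 1) = Φ(−2/SD) | 0.187 | 0.212 |
| P(score ≤ 2) = Φ(−1/SD) | 0.328 | 0.345 |
| P(score ≤ 4) = Φ(1/SD) | 0.672 | 0.655 |
| P(score ≤ 5) = Φ(2/SD) | 0.813 | 0.788 |

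The cumulative probability passes 0.25 at a score of 2 and 0.75 at a score of 5, so the interquartile range is 2 to 5 at either SD. A lower quartile of 1 would need an SD above 2 / 0.6745 = 2.97. Rounding down gives 1 to 5, but it also gives medians of 1 and 3, against the printed 2 and 4. The lower group's range of 0 to 3 is correct at both SDs. The printed medians are not errors, because 1.5 and 3.5 lie on rounding boundaries.

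**The case against.** Four points can be made for the plan.

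- **An interchange is not proven.** The simulation's sidedness is not stated, and a one-sided test at the printed SD of 2.5 gives 89.8%, as close to 89.5% as the SD 2.25 result. This stands: the interchange is an inference. It does not rescue the text, because the t-test is stated to be two-sided and its 86% at SD 2.25 remains wrong. A one-sided simulation could not confirm a two-sided calculation either.
- **The two SDs may describe different quantities.** The simulation SD applies before rounding and bounding. With an input of 2.5, the bounded scores have SDs of about 1.95 and 2.34 and a mean difference of about 1.67 (3.586 − 1.916). Different SDs could therefore be deliberate. That is fair, and a reason to label the SD clearly, but 89.5% still does not follow from the printed input of 2.5.
- **Part of the gap between the tests comes from bounding.** On the same bounded scores the t-test exceeds the Mann-Whitney by only about 0.8 point at SD 2.5 (83.6% against 82.8% in a 200,000-trial run). This is correct. Against the plan's unbounded t-test formula the shortfall is 1.7 to 3.4 points. On neither comparison does the rank test come out ahead, as printed.
- **The practical effect is small.** Power exceeds 80% at either SD, the plan sets no target power, and no analysis depends on the quartile. This also stands, and limits the remedy to restating the figures.

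**Conclusion.** The concern holds. Under a two-sided 5% test, neither printed power follows from its printed SD.

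- **If SD 2.25 is intended,** the t-test power is 92.3%, so the stated 86% is 6.3 points too low. The simulated 89.5% is essentially right.
- **If SD 2.5 is intended,** the t-test's 86% is right. The Mann-Whitney power is 82.7–83.9%, so the stated 89.5% is 5.6 to 6.8 points too high.

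The type II error of the planned test is thus about 10% or about 17%, and the documents do not settle which. The lower quartile of the mean-3.5 group is wrong at either SD. Whether the summaries still agree with the source trial cannot be judged from the documents.

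The conclusion assumes that the simulation used 30 per group and a two-sided 5% test, as the t-test calculation does. It should be corrected because these figures are the entire sample size argument, but it does not threaten the design.

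**What to change.** In the Statistical Analysis part of section 9:

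1. Declare one SD for both calculations, with its basis in the cited trial, and say that in the simulation it applies before rounding and bounding.
2. Restate both powers at that SD: t-test 86% and Mann-Whitney about 83% at SD 2.5, or t-test 92% and Mann-Whitney about 90% at SD 2.25.
3. State that the simulated test was two-sided at 5% with 30 per group, and how out-of-range scores were handled. If the original run was one-sided, rerun it two-sided.
4. Correct the interquartile range of the mean-3.5 group to 2 to 5, then recheck the sentence claiming consistency with the source trial.

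The cost is wording only: sample size, test, alpha and endpoint are unchanged. The one downside is that, if SD 2.5 is the intended value, the stated Mann-Whitney power falls from 89.5% to about 83%.

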6. SPECIFIC AIMS

The ultimate objective of the proposed line of research is to determine if cryoanalgesia is an effective adjunctive treatment for pain in the period immediately following various painful surgical procedures; and, if this analgesic modality decreases the risk of persistent postoperative pain, or "chronic" pain. *The objective of the proposed pilot study is to optimize the protocol and collect data to power subsequent, definitive clinical trials.*

Specific Aim 1: To determine if, compared with current and customary analgesia, the addition of cryoanalgesia decreases the incidence and severity of post-surgical pain.

Hypothesis 1a (primary): The severity of surgically-related pain will be significantly decreased on postoperative day 2 with the addition of cryoanalgesia as compared with patients receiving solely standard-of-care treatment.

Hypothesis 1b: The incidence of chronic pain will be significantly decreased one year following surgery with the addition of cryoanalgesia as compared with patients receiving solely standard-of-care treatment.

Hypothesis 1c: The severity of chronic pain will be significantly decreased one year following surgery with the addition of cryoanalgesia as compared with patients receiving solely standard-of-care treatment.

[figure not shown]
Specific Aim 2: To determine if, compared with current and customary analgesia, the addition of cryoanalgesia improves postoperative functioning.

Hypothesis 2a: Following primary unilateral knee and shoulder arthroplasty as well as rotator cuff repair, joint range of motion will be significantly increased within the year following surgery with the addition of cryoanalgesia as compared with patients receiving solely standard-of-care treatment.

Hypothesis 2b: Following video-assisted thoracoscopic surgery, inspiratory spirometry will be improved within the month following surgery with the addition of cryoanalgesia as compared with patients receiving solely standard-of-care treatment.

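### The specific aims and the statistical analysis section disagree about which results are confirmatory, and the secondary tests have no order, adjustment or exploratory label

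*Combined protocol and SAP*

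**What the plan says.** Section 6 (Specific Aims) lists five hypotheses for the whole study population:

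- "Hypothesis 1a (primary): The severity of surgically-related pain will be significantly decreased on postoperative day 2". No operation is named.
- For 1b: "The incidence of chronic pain will be significantly decreased one year following surgery with the addition of cryoanalgesia". Hypothesis 1c says the same of severity. Neither is limited to one operation.
- 2a makes a significance claim about range of motion after knee, shoulder and rotator cuff surgery. 2b concerns thoracoscopic surgery and says only that spirometry will improve.

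The Statistical Analysis part of section 9 takes a narrower position. The cohorts other than mastectomy are pilots with no primary endpoint or statistical plan set beforehand. For mastectomy, the average pain score on postoperative day 2 is the primary outcome, and the plan expects a conclusive answer on acute pain only. A chronic pain endpoint is left to a later trial, "which will require far more subjects than we will enroll for the current study".

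For everything else, section 9 says: "Differences between groups in demographic variables and secondary endpoints will be assessed with the Mann-Whitney U test for continuous or ordinal data", with Fisher's exact test for categorical data. It gives these tests no significance level, order, adjustment or exploratory label. The only level in the document, two-sided 5%, belongs to the power statement for the primary: "n=30 patients per group provide 86% power".

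**The concern.** The two sections answer the same question differently: which results may be reported as having confirmed a hypothesis? Under section 6, a p-value below 0.05 for chronic pain at one year would meet a stated hypothesis. Under section 9, the study is too small for that conclusion. Nothing in the analysis text settles the matter, because the secondary tests have neither a rule that controls their error rate nor a label that removes them from inference.

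The plan also does not say which month-12 variable answers 1b or 1c. The assessment schedule offers several, so the choice could be made after the data are seen.

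What is at stake is a claim that cryoneurolysis prevents chronic pain. Section 7 says that such a demonstration by this study would have a large and immediate effect on patients, so the risk of a chance finding being presented this way is not trivial.

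**Working it through.** **1. The plan's own error figure.** Section 9 reports a simulated Type I error of 4.85% for the single primary test. Repeating the simulation (rounded normal scores kept within 0 to 10, SD 2.5, 30 per group, Mann-Whitney U, 10,000 trials) gives 4.3% with both means at 1.5 and 4.8% with both at 3.5. The primary test therefore holds its level. The figure says nothing about the secondary tests.

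The 86% power does not follow from the stated inputs. A difference of 2 and an SD of 2.25 give 92.3% by the two-sample t-test, whereas an SD of 2.5 gives 86.1%. The two SDs in section 9 need reconciling, but this is a separate matter and does not bear on multiplicity.

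**2. The two sections side by side.**

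| Item | Section 6 | Section 9 |
|---|---|---|
| 1a, day-2 pain | Primary, all operations | Primary in mastectomy only; of most interest, without a plan, in shoulder arthroplasty and skin grafting |
| 1b, 1c, one-year pain | Significance claims, all operations | Needs a much larger trial |
| 2a, range of motion | Significance claim | Pilot cohorts, no plan fixed in advance |
| 2b, spirometry | Improvement, no significance claim | Pilot cohort, no plan fixed in advance |

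Only 1b and 1c are secondary hypotheses that apply to mastectomy.

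**3. Error for 1b and 1c in mastectomy.** Assume each test is made at two-sided 5%. With one variable per hypothesis and independent tests:

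1 − 0.95² = 9.75%.

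**4. Error if the month-12 variable is left open.** The schedule offers two candidates for 1b (phantom incidence, wound incidence). It offers five for 1c (average and worst phantom pain, average and worst wound pain, Brief Pain Inventory composite). That makes seven:

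1 − 0.95⁷ = 30.2% if independent.

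Positive correlation between the tests lowers both figures. The documents give no correlations.

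**5. Upper end: every schedule cell tested in mastectomy.**

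- Opioid consumption: 12
- Average and worst pain score, days 0 to 21: 2 × 8 − 1 (the primary) = 15
- Inventory composite: 4
- Phantom pain, four measures × four months: 16
- Wound pain, four measures × four months: 16
- Difficulty sleeping, awakenings, nausea: 3 × 7 = 21 (seven marks per row in the extracted table, which may be imperfect)
- Cancer recurrence: 1

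The total is 85. The expected number of false positives under no effect is 85 × 0.05 = 4.25, whatever the correlation.

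Fisher's exact test is conservative. With 30 per arm its true size is about 0.1% to 2.7% for event rates between 5% and 70%. If 16 of the 85 tests are binary (8 incidence, 7 difficulty sleeping, 1 recurrence), the expected number is 69 × 0.05 = 3.45 plus 16 × 0.001 to 16 × 0.027, or about 3.5 to 3.9.

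The chance of at least one false positive among 85 depends heavily on an assumed common correlation: 92% at 0.3, 74% at 0.5, 48% at 0.7 and 22% at 0.9.

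**6. Why Bonferroni is not the answer.** Dividing 5% by 85 gives 0.00059 per test. With 30 per group, t-test power for a 2-point difference would be about 43% (SD 2.25) or 31% (SD 2.5).

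**The case against.** The strongest defence is that the plan already contains the restraint being asked for. It calls itself a pilot, confines its conclusive result to one acute endpoint in one cohort, and sends chronic pain to a later trial. Its primary test is a single comparison specified in advance. All of that is correct, and it keeps the point modest. But stating what is powered does not stop 1b or 1c being declared met at p<0.05, and section 6 is worded so that they could be.

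Four stronger readings are tempting, and the documents do not support them:

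- A reader might infer that 85 secondary tests are planned, each at 5%. The schedule shows when data are collected. Section 9 names a test for each type of endpoint without saying that every time point is tested, and it sets no level for these tests.
- A reader might infer that a false positive is close to certain. That requires independence or weak correlation, and measurements repeated on the same patients are correlated.
- A reader might take all of 1b to 2b as significance claims in mastectomy. 2b makes no such claim, and 2a and 2b concern other operations.
- A reader might infer from section 6 that 1a will be tested as primary in every cohort. Section 9 sets out no such analysis.

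It is also fair to say that day-by-day results need not give way to subject means. They show the time course, which matters for a block said to last several weeks, and a mean over several months would not match hypotheses set at one year.

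**Conclusion.** The point holds as an inconsistency over which results are confirmatory, together with an open family of secondary tests. It should be corrected, but it does not threaten the primary mastectomy comparison.

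In mastectomy, the chance of at least one false claim on chronic pain is 9.75% with one variable for each of 1b and 1c, and about 30% if any of seven month-12 variables may serve. Both figures assume a 5% level for secondary tests, no true effect and independence; positive correlation and the conservatism of Fisher's test make them smaller. The figure of about four expected false positives applies only if every schedule cell is tested, and is somewhat lower once Fisher's test is allowed for.

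**What to change.** 1. In section 6, limit the primary label on Hypothesis 1a to mastectomy, and reword 1b, 1c and 2a as estimates or exploratory questions so that they agree with section 9.
2. In the Statistical Analysis part of section 9, state that all comparisons other than the mastectomy primary are exploratory and will be reported as estimates with confidence intervals, without significance claims. Day-by-day results may stay in that form.
3. If a chronic pain claim is wanted in mastectomy, name one month-12 variable for 1c and one for 1b. Test 1c and then 1b after the primary, each at two-sided 5% and only if the preceding test is met. This takes no alpha from the primary.

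The changes are to text only, with no added subjects or visits, though the choice of the two month-12 variables must be made before the data are unmasked. The cost is that fewer results can be called significant.
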